10.2.1 Serious Adverse Events

Adverse events are classified as serious or non-serious.

A serious adverse event is any AE that is:

- fatal
- life-threatening
- requires or prolongs hospital stay
- results in persistent or significant disability or incapacity
- a congenital anomaly or birth defect
- an important medical event

Important medical events are those that may not be immediately life threatening, but are clearly of major clinical significance. They may jeopardize the subject, and may require intervention to prevent one of the other serious outcomes noted above. For example, drug overdose or abuse, a seizure that did not result in in-patient hospitalization, or intensive treatment of bronchospasm in an emergency department would typically be considered serious.

All adverse events that do not meet any of the criteria for serious should be regarded as non-serious adverse events.

Events of progression of the subject's underlying cancer as well as events clearly related to progression of the subject's cancer (signs and symptoms of progression) should not be reported as a serious adverse event.

Hospitalization, Prolonged Hospitalization or Surgery.

Any adverse event that results in hospitalization or prolonged hospitalization should be documented and reported as a serious adverse event unless specifically instructed otherwise in this protocol. Any condition responsible for surgery should be documented as an adverse event if the condition meets the criteria for an adverse event.

Neither the condition, hospitalization, prolonged hospitalization, nor surgery are reported as an adverse event in the following circumstances:

- Hospitalization or prolonged hospitalization for diagnostic or elective surgical procedures for a preexisting condition. Surgery should not be reported as an outcome of an adverse event if the purpose of the surgery was elective or diagnostic and the outcome was uneventful.
- Hospitalization or prolonged hospitalization required to allow efficacy measurement for the study.
- Hospitalization or prolonged hospitalization for therapy of the target disease of the study, unless it is a worsening or increase in frequency of hospital admissions as judged by the clinical investigator.

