10.1 Adverse Events

An *adverse event* (AE) is any symptom, sign, illness or experience that develops or worsens in severity during the course of the study. Intercurrent illnesses or injuries should be regarded as adverse events. Abnormal results of diagnostic procedures are considered to be adverse events if the abnormality:

- results in study withdrawal
- is associated with a serious adverse event
- is associated with clinical signs or symptoms
- leads to additional treatment or to further diagnostic tests is considered by the investigator to be of clinical significance

Adverse Event Reporting Period

The study period during which adverse events must be reported is defined as the period from the initiation of the first study treatment to 30 days following the last administration of study treatment.

Post-study Adverse Event.

All unresolved adverse events should be followed by the investigator until the events are resolved, the patient is lost to follow-up, or the adverse event is otherwise explained. At the last scheduled visit, the investigator should instruct each patient to report any subsequent event(s) that the patient, or the patient's personal physician, believes might reasonably be related to participation in this study.

Abnormal Laboratory Values.

A clinical laboratory abnormality should be documented as an adverse event if the abnormality is of a degree, typically at least grade 2 and not present as grade 1 or better at baseline, that requires active management; e.g. change of dose, discontinuation of the drug, more frequent follow-up assessments, further diagnostic investigation.

10.2 Recording of Adverse Events.

At each contact with the subject, the investigator must seek information on adverse events by specific questioning and, as appropriate, by examination. Information on all adverse events should be recorded immediately in the source document, and also in the appropriate adverse event module of the case report form (CRF). All clearly related signs, symptoms, and abnormal diagnostic procedures results should be recorded in the source document, though should be grouped under one diagnosis.

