10.3 Assessment of Adverse Events

All AEs and SAEs whether volunteered by the subject, discovered by study personnel during questioning, or detected through physical examination, laboratory test, or other means will be reported appropriately.

The severity rating of an AE refers to its intensity. The severity of each AE will be determined by the Investigator using the NCI CTCAE (cite version here). For any term that is not specifically listed in the CTCAE scale, severity should be assigned a Grade of 1 through 5 using the following CTCAE guidelines:

Grade 1:	Mild; asymptomatic or mild symptoms; clinical or diagnostic observations only; intervention not indicated
Grade 2:	Moderate; minimal, local or noninvasive intervention indicated; limiting age appropriate instrumental activities of daily living
Grade 3:	Severe or medically significant but not immediately life-threatening; hospitalization or prolongation of hospitalization indicated; disabling; limiting self- care activities of daily living
Grade 4:	Life-threatening consequences; urgent intervention indicated
Grade 5:	Fatal

Each reported AE or SAE will be described by its duration (i.e., start and end dates), regulatory seriousness criteria if applicable, suspected relationship to the study drug (see following guidance), and actions taken. To ensure consistency of AE and SAE causality assessments, only the PI or sub-investigators may grade AEs, and investigators should apply the following general guideline:

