10.3.5 Preexisting Medical Conditions

A preexisting medical condition is one that is present at the start of the study. Such conditions should be reported as medical and surgical history. A preexisting medical condition should be re-assessed throughout the trial and reported as an AE or SAE only if the frequency, severity, or character of the condition worsens during the study. When reporting such events, it is important to convey the concept that the preexisting condition has changed by including applicable descriptors (e.g., "more frequent headaches").

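### Read literally, 10.2.1 exempts a worsened preexisting condition from AE reporting when the admission is diagnostic or elective, which conflicts with 10.1 and 10.3.5, and nothing says which section prevails

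*Combined protocol and SAP*

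**What the plan says.** The exemption is in 10.2.1, under hospitalization, prolonged hospitalization or surgery. Its lead sentence reads "Neither the condition, hospitalization, prolonged hospitalization, nor surgery are reported as an adverse event in the following circumstances". Three circumstances follow.

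- The first is "Hospitalization or prolonged hospitalization for diagnostic or elective surgical procedures for a preexisting condition". It says nothing about worsening.
- The second is admission needed to measure efficacy.
- The third is admission to treat the target disease. It carries an exception: "unless it is a worsening or increase in frequency of hospital admissions as judged by the clinical investigator".

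The sentence immediately before the exemption says: "Any condition responsible for surgery should be documented as an adverse event if the condition meets the criteria for an adverse event".

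Elsewhere, 10.1 defines an AE as "any symptom, sign, illness or experience that develops or worsens in severity during the course of the study". Section 10.3.5 asks investigators to look at preexisting conditions again as the study goes on, each being "reported as an AE or SAE only if the frequency, severity, or character of the condition worsens during the study". Section 10.2 requires every AE in the study period to be recorded.

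Safety and tolerability is one of the two primary objectives (1.1, 11.2). Section 11.5 analyses it by tabulating each toxicity at its worst grade and giving the rate of grade 3 or higher toxicity with an exact 95% confidence interval.

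**The concern.** The lead sentence goes further than a usual carve-out for planned admissions in two ways. It exempts the condition as well as the admission, and it removes AE status, not only SAE status. Because the third bullet has a worsening exception and the first does not, a reader could take the difference as deliberate.

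The case in question is a preexisting condition that deteriorates on treatment and leads to admission for a diagnostic or elective procedure. For example, 3.2 admits patients whose atrial fibrillation has been controlled for more than 30 days. If it worsens and the patient is admitted for a diagnostic cardiac procedure, 10.1 and 10.3.5 make it an AE, while the words of 10.2.1 say it is not reported as one.

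Three things depend on that classification: the AE module of the case report form, and so the toxicity rate in 11.5; the 24-hour SAE report to the manufacturer (10.4); and the medical monitor's real-time review of unexpected, related SAEs (10.6).

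**Working it through.** **Step 1: the rules side by side.** Take a preexisting condition that worsens on study and leads to a diagnostic or elective admission.

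- 10.1: the event worsened in severity during the study, so it is an AE.
- 10.3.5: its frequency, severity or character has worsened, so it is reported as an AE or SAE.
- 10.2.1, general rule: an AE that leads to hospitalization is an SAE, unless the protocol specifically instructs otherwise.
- 10.2.1, first exempt circumstance: read literally, neither the condition nor the admission is reported as an AE.

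The exemption can be read as the specific instruction that the general rule allows for. Section 10.2 does not settle the matter, because it requires AEs to be recorded and the question is whether this event counts as one. No section states precedence.

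**Step 2: the design figures the plan does state.** The plan gives no expected toxicity rate or interval width, so the only figures to reproduce are those of the response design in 11.4 (at most 1 of 10 stops the trial; at least 6 of 29 is positive; 10% against 30%).

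- Probability of early termination at 10%: 0.9^10 + 10 × 0.1 × 0.9^9 = 0.3487 + 0.3874 = 0.7361 (stated 0.74).
- Probability of a positive result: the sum over x = 2 to 10 of P(X1 = x) × P(X2 ≥ 6 − x), with X1 ~ Bin(10, p) and X2 ~ Bin(19, p). At p = 0.10 this is 0.0471 (stated no more than 0.05). At p = 0.30 it is 0.8051 (stated at least 0.80).

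All three reproduce. None depends on AE classification, so the go/no-go rule is not touched.

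**Step 3: sensitivity of the toxicity rate.** If one patient's only toxicity of grade 3 or higher is omitted, the rate falls by 1/n. That is 1/29 = 3.4 points at full accrual, or 1/10 = 10 points if the trial stops after stage 1. The exact 95% limits are Beta quantiles: lower = B(0.025; x, n − x + 1), upper = B(0.975; x + 1, n − x). The counts below are assumptions chosen to show a range, since the documents give none.

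| Assumed true count | One omitted | Two omitted |
|---|---|---|
| 12/29 = 41.4% (23.5 to 61.1) | 11/29 = 37.9% (20.7 to 57.7) | 10/29 = 34.5% (17.9 to 54.3) |
| 9/29 = 31.0% (15.3 to 50.8) | 8/29 = 27.6% (12.7 to 47.2) | 7/29 = 24.1% (10.3 to 43.5) |
| 6/29 = 20.7% (8.0 to 39.7) | 5/29 = 17.2% (5.8 to 35.8) | not shown |
| 3/10 = 30% (6.7 to 65.2) | 2/10 = 20% (2.5 to 55.6) | 1/10 = 10% (0.3 to 44.5) |

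At n = 29 the shift from one omission is small beside the width of the interval, but it always runs in the favorable direction.

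**The case against.** The strongest reply is that the sections can be read together. The sentence before the exemption keeps a condition responsible for surgery reportable when it meets the AE criteria. The rest of the first bullet says an uneventful elective or diagnostic operation is not listed as the outcome of an AE, which presupposes that an AE may already be on record. Section 10.3.5 is the section written for preexisting conditions, and it asks for reporting on worsening. On that reading the first bullet covers only unchanged conditions.

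This reply has force. A reader might infer that 10.2.1 expressly excludes conditions that have worsened. It does not: that reading comes from the bullet's silence, and the surrounding text leans the other way. What remains is that the harmonized reading is available but not required. The exemption follows directly on the sentence about surgery and can be taken as its exception, and the third bullet shows that a worsening clause was written where one was wanted.

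A reader might also infer that grade 3 events are being dropped from the primary rate. The documents do not support that either. The descriptor "hospitalization or prolongation of hospitalization indicated" is one of several for grade 3, and the scale it belongs to is for terms not listed in CTCAE. An elective or diagnostic admission does not by itself make an event grade 3. Because 11.5 uses the worst grade across cycles and covers all observed toxicities, a patient leaves the rate only when the omitted event was that patient's sole toxicity of grade 3 or higher.

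Finally, some signals have other routes. Newly arising lung, cardiac or retinal toxicity is not a preexisting condition. ECGs are done each cycle and echocardiograms about every 12 weeks (section 8.0), eye findings go to a dedicated form (5.3.1), and retinal vein occlusion is reported as an SAE (Table 4). Section 3.2 also screens out several cardiac conditions and prior retinal vein occlusion. These points narrow the exposure. They do not settle how a worsened preexisting condition is to be classified.

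**Conclusion.** The concern holds as a conflict on the literal wording that the documents leave unresolved. The same worsened preexisting condition can be an AE or SAE under 10.1 and 10.3.5 and exempt under 10.2.1. Some such events may therefore be left out of SAE reporting and out of the primary toxicity rate.

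The size cannot be stated as an expected bias, because the documents give no frequency for such admissions. What can be stated is the effect per patient: 3.4 points at n = 29 and 10 points at n = 10. This assumes that all enrolled patients are treated and form the denominator, and that the omitted event was the patient's only toxicity of grade 3 or higher. No threshold or stopping rule is attached to the toxicity rate, and the Simon decision on response does not change.

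The wording should be reconciled because it bears on SAE capture and a primary safety objective, and because the repair is almost free. It is not evidence that the analysis in section 11 is wrong.

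**What to change.** Keep the lead sentence of 10.2.1 as it is. Add an exception to the first bullet, along these lines: *unless the condition has worsened in frequency, severity or character since baseline (see 10.3.5), in which case the condition is recorded and graded as an AE, and as an SAE if a seriousness criterion is met.*

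Deleting the reference to the condition from the lead sentence would be too broad. That sentence governs all three bullets, so the deletion would also alter the exemptions for efficacy measurement and for treatment of the target disease.

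Planned admissions for an unchanged condition stay exempt. Sample size, type I error and power do not change. The cost is one clause, a few more AE or SAE reports, and a toxicity rate that may be slightly higher.

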10.3 Assessment of Adverse Events

All AEs and SAEs whether volunteered by the subject, discovered by study personnel during questioning, or detected through physical examination, laboratory test, or other means will be reported appropriately.

The severity rating of an AE refers to its intensity. The severity of each AE will be determined by the Investigator using the NCI CTCAE (cite version here). For any term that is not specifically listed in the CTCAE scale, severity should be assigned a Grade of 1 through 5 using the following CTCAE guidelines:

Grade 1:	Mild; asymptomatic or mild symptoms; clinical or diagnostic observations only; intervention not indicated
Grade 2:	Moderate; minimal, local or noninvasive intervention indicated; limiting age appropriate instrumental activities of daily living
Grade 3:	Severe or medically significant but not immediately life-threatening; hospitalization or prolongation of hospitalization indicated; disabling; limiting self- care activities of daily living
Grade 4:	Life-threatening consequences; urgent intervention indicated
Grade 5:	Fatal

Each reported AE or SAE will be described by its duration (i.e., start and end dates), regulatory seriousness criteria if applicable, suspected relationship to the study drug (see following guidance), and actions taken. To ensure consistency of AE and SAE causality assessments, only the PI or sub-investigators may grade AEs, and investigators should apply the following general guideline:

10.3.1 Relationship to study drug: Yes

There is a plausible temporal relationship between the onset of the AE and administration of the study drug, and the AE cannot be readily explained by the subject's clinical state, intercurrent illness, or concomitant therapies; and/or the AE follows a known pattern of response to the study drug; and/or the AE abates or resolves upon discontinuation of the study drug or dose reduction and, if applicable, reappears upon re-challenge.

10.3.2 Relationship to study drug: No

Evidence exists that the AE has an etiology other than the study drug (e.g., preexisting medical condition, underlying disease, intercurrent illness, or concomitant medication); and/or the AE has no plausible temporal relationship to study drug administration (e.g., cancer diagnosed 2 days after first dose of study drug).

Suspected unexpected serious adverse reactions (SUSARs) will be collected and reported by the Sponsor and/or designee to the competent authorities and relevant ethics committees in accordance with Directive 2001/20/EC or as per national regulatory requirements in participating countries.

Expected adverse events are those adverse events that are listed or characterized in the Package Insert or current Investigator Brochure.

Unexpected adverse events are those not listed in the Package Insert (P.I.) or current Investigator Brochure (I.B.) or not identified. This includes adverse events for which the specificity or severity is not consistent with the description in the P.I. or I.B. For example, under this definition, hepatic necrosis would be unexpected if the P.I. or I.B. only referred to elevated hepatic enzymes or hepatitis.

10.3.3 Diagnosis vs. Signs and Symptoms

If known at the time of reporting, a diagnosis should be reported rather than individual signs and symptoms (e.g., record only liver failure or hepatitis rather than jaundice, asterixis, and elevated transaminases). However, if a constellation of signs and/or symptoms cannot be medically characterized as a single diagnosis or syndrome at the time of reporting, it is ok to report the information that is currently available. If a diagnosis is subsequently established, it should be reported as follow-up information.

10.3.4 Deaths

All deaths that occur during the protocol-specified AE reporting period (see Section 10.2), regardless of attribution, will be reported to the appropriate parties. Of note, if a death occurs due to progression without an accompanied adverse event, reporting to the drug manufacturer is not required. When recording a death, the event or condition that caused or contributed to the fatal outcome should be reported as the single medical concept. If the cause of death is unknown and cannot be ascertained at the time of reporting, report "Unexplained Death".

10.3.5 Preexisting Medical Conditions

A preexisting medical condition is one that is present at the start of the study. Such conditions should be reported as medical and surgical history. A preexisting medical condition should be re-assessed throughout the trial and reported as an AE or SAE only if the frequency, severity, or character of the condition worsens during the study. When reporting such events, it is important to convey the concept that the preexisting condition has changed by including applicable descriptors (e.g., "more frequent headaches").

10.3.6 Pregnancy

Pregnancy itself is not regarded as an AE unless there is a suspicion that the study medication may have interfered with the effectiveness of the contraceptive medication. If a female subject becomes pregnant while receiving investigational therapy or within 120 days after the last dose of study drug, a report should be completed and submitted to Array within 24 hours of learning of its occurrence.

Subjects who become pregnant during the study will not receive any additional study medication and will be withdrawn from the study. The Investigator must strongly encourage these subjects to return to the study site for the final protocol-specified visit and assessments. Follow-up to obtain the outcome of the pregnancy should also occur. Abortion, whether accidental, therapeutic, or spontaneous, should always be classified as serious, and expeditiously reported as an SAE. Similarly, details of the birth, and the presence or absence of any congenital anomaly/birth defect or maternal and/or newborn complications in a child born to a female subject exposed to the study drug should be reported as an SAE.

10.4 SAE Reporting to Array

All serious adverse events, regardless of suspected causality, occurring after the patient has provided the main informed consent and until at least 30 days after the patient has stopped study treatment must be reported to Array within 24 hours of learning of its occurrence. Send the completed, signed SAE report to the oncology Array Drug Safety and Epidemiology (DS&E) department ([contact]).

Any serious adverse event that occurs after the 30 days study period should only be reported to Array if the investigator suspects a causal relationship to the study treatment. Recurrent episodes, complications, or progression of the initial SAE must be reported as follow-up to the

original episode within 24 hours of the investigator receiving the follow-up information. An SAE occurring at a different time interval or otherwise considered completely unrelated to a previously reported one should be reported separately as a new event.

Other reportable events:

Deviations:

An one-time accidental or unintentional deviation from the approved protocol, identified retrospectively, that in the opinion of the investigator or as defined by the protocol, placed one or more participants at increased risk, compromises the rights or welfare of subjects, and/or disrupts the study design, is considered a reportable event and must be reported to the Study Principal Investigator, Study Medical Monitor, IRB, and ACC DSMC within 5 business days of knowledge. Principal Investigator and Medical Monitor approval/acknowledgement must be received first and included in with the IRB/DSMC submission.

Deviations to protect subjects from immediate harm/danger should be reported immediately following the event to the entities outlined above.

Exceptions:

An exception is defined as a one-time, intentional action or process that departs from the IRB and CTSRMC approved study protocol, intended for one occurrence. AND this action disrupts the study progress, such that the study design or outcome (endpoints) may be compromised, or the action compromises the safety and welfare of study subjects (i.e. requests to enroll and/or treat subjects outside of the current protocol criteria). Exceptions that meet this criteria will not be allowed unless reviewed and approved first by the Study Medical Monitor and the Study Principal Investigator/Sponsor-Investigator, and then subsequently by the ACC DSMC, and UPenn IRB prior to this subject being enrolled/treated. PI/Sponsor-Investigator and Medical Monitor approval must be received first and included in with the IRB/DSMC submission. All entities should be given sufficient time to evaluate this request.

Examples of Exceptions/Deviations that require submission include:

- Stopping rules that were not completed per protocol
- Dosing errors

Exceptions to eligibility, treatment/dosing, contraindicated treatment/therapies/interventions or safety tests will not be approved.

Events not deemed reportable as outlined above will require a PI assessment regarding study and/or safety impact. This assessment should be documented appropriately.

